4. DEFINITION OF OUTCOMES

Diarrheal visit: A diarrheal visit is defined as a visit for care of diarrhea in which the patient described:

- 3 or more loose or liquid stools; or
- At least 1 bloody stool; or
- 1-2 or an indeterminate number of loose or liquid stools and exhibited at least some dehydration

Diarrhea episode: A diarrheal episode is defined as:

- All diarrheal visit(s) for which the date of onset for a diarrheal visit was less than or equal to 7 days from the date of discharge for the previous visit, constitute a single “diarrheal episode”.
- The onset of a diarrheal episode was defined as the day on which it was reported to have begun for the first visit of the episode.

Cholera episode: A cholera episode is defined as:

- A diarrheal episode in which no component visit was described as bloody diarrhea; and

- A fecal specimen from at least one component visit yielded *V. cholerae* 01 in the ICDDR,B laboratory; and
- An identity check performed after discharge for the visit in which *V. cholerae* 01 was isolated, confirmed that the person whose name was given at the treatment center had indeed sought care for diarrhea on the date of presentation

5. OTHER DEFINITIONS

Zero time: The date of dose for the dose recipients and the start date of the mass vaccination (January 10, 2014) for non-dose recipients.

Complete dose recipients: Individuals who drank and swallowed one complete dose (the full course).

Incomplete dose recipients: Individuals who swallowed any amount of dose but not completed the full course.

No-dose recipients: Individuals who were present at zero time but not dosed. During routine demographic updates, individuals were identified as entered into the population prior to dosing and therefore would have been eligible at the time of vaccination. These individuals are also considered as the no-dose recipients.

Two-dose recipients: Individuals found to have taken two doses based on the vaccine record book.

Lost to follow up: Individuals who died or moved out of the study area from the resident any time after zero time. Note that internal migration out demographic events will not be considered as lost to follow-up.

Duration of follow up period: The time between 7 and 180 days after the zero time.

Pre-dosing period: The period on or before the zero time. Events whose onsets occur in this period will not be considered in the analysis.

Post dose interval: The interval between the zero time and 7 days from zero time. Cholera events whose onsets occur in this period will not be considered in the analysis.

Post follow up period: The time after the completion of the follow up period. Events whose onsets occur in this period will not be considered in the analysis.

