We will use the killed whole cell oral cholera vaccine, Shanchol™ as well as an oral placebo for the study. The vaccine is manufactured by Shantha Biotechnics, in Hyderabad, India and registered in India and is prequalified by the WHO. Shanchol™ is available in a single dose vial. The study agents will be supplied by the company and imported by approaching the Directorate General of Drug Administration of Bangladesh. Both the vaccine and placebo will be transported from the manufacturer to a designated EPI cold room at Mohakhali, Dhaka arranged for this study where it will be stored. We will identify vaccination centers within the intervention areas. These sites may include the government's EPI outposts, non-government facilities utilized during national immunization days, or other appropriate facilities which are easily accessible by the target population (Appendix 1C). Study agents will be maintained at 2-8°C. Immunization will be carried to the study population in three phases. Vaccination teams composed of the required number of vaccinators, record keepers, consent takers, supervisors, and other support staff will be present at each vaccination site (approximately 30 sites). Each participant over

the age of one year and non pregnant females living in communities will be individually randomized to receive vaccine or placebo.

Pregnancy status will be enquired verbally for all married women of child bearing age during the census update as well as before vaccination to exclude them from the study. If she is uncertain about her pregnancy status, she will be asked for her last menstrual period (LMP). All married females will be asked about their last LMP, if this is more than four weeks prior, irregular, or unknown, will be considered ineligible for the study. Pregnancy status in married women will also be ascertained at least two months after vaccination by home visits of trained field staff. Those who will be confirmed for pregnancy at this time point will be followed up at 6 months as well as with further visits monthly to ascertain pregnancy outcome after delivery. A pregnancy followup questionnaire will be used after consent taking for these visits (Appendix 6A, 6 B).

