The residence of all participants who were culture confirmed for cholera will be visited within 14 days by a health worker to confirm the identity of the patient. An identity confirmation form will be used where the patient's demographic address and date of presentation will be recorded from the surveillance database. The interviewer will ask whether the person sought treatment for diarrhea at the clinic on the date mentioned in the form. This follow-up visit will also be carried out to assess clinical progress and cholera-related disability (Appendix 5).

Immunological assays using blood specimens from study participants:

Blood: Immunological analyses will be conducted in a small subgroup of patients as has carried out earlier in the feasibility study of oral cholera vaccine (icddr,b protocol # 10061). For this purpose, a

sample size of 324 participants is needed for an adequately powered sample. To account for unblocked unique number coding, we plan on enrolling 500 participants (less than 5 years, 5 to less than 15 years and 15 years of age or older; so as to obtain at least 108 in each age group) from the vaccination sites. Necessary consent and blood draw forms will be filled up (Appendix 3A-C). Venous blood (2-5ml) will be collected from these participants prior to immunization and 14 days after intake of the study agent (day 0 and day 14). Participants will be given a 2 day window for their 14 day blood draw (+/-2 days).

The blood samples will be transported to the laboratory (within 6 hours of collection). At the laboratory, plasma will be separated and stored at -20 degree C until tested. Technicians unaware of the codes of the agents received by the trial participants will test in random order paired plasma samples for vibriocidal antibody titres and different isotype of LPS specific antibodies (IgA, IgG and IgM) by ELISA.

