- Date of onset for first episode of watery diarrhea with severe dehydration detected in the study treatment centres from 7days to,6, 12,18and 24 months, respectively after dosing among those who received 1 dose of vaccine or placebo
- Date of onset for first episode of diarrhea with fecal excretion of *V. cholerae*O1 in non-participating subjects, who are detected within one of the study treatment centres from 7 daysup to 6,12,18and 24 monthsafter dosing of study participants.
- Date of onset for first episode of diarrhea with severe dehydration and fecal excretion of *V. cholerae*O1 in non-participating subjects, who are detected within one of the study treatment centres from 7 daysup to 6,12,18and 24 monthsafter dosing of study participants.

Secondary safety endpoints

- Number of adverse events and serious adverse events in participants who received 1 dose of vaccine or placebo and present for care of vaccine adverse effects at treatment settings or who die from the time of dosing until 28 days later (passive surveillance by type of complaint and by cause of death).

Secondary immunogenicity endpoints

- Geometric mean serum vibriocidal (to El Tor Inaba and Ogawa O1 serogroup organisms and to O139 serogroup organisms) titers measured in participants at baseline (day0) and 14 days after receipt of either vaccine or placebo.
- Four-fold or greater rises in titers of serum vibriocidal antibodies (to El Tor Inaba and Ogawa O1 serogroup organisms and to O139 serogroup organisms), relative to baselineday 0 and 14 two days after receipt of either vaccine or placebo

Analysis plan

To analyze vaccine protection, we will use Cox proportional hazard regression models verifying first that the proportionality assumption is satisfied for all independent variables. Checking of the proportional hazard assumption will be performed by plotting the observed standardized score with simulated realizations for each covariate in the model, and the p-value will be derived from the Kolmogorov-type supremum test based on 1,000 simulations. If a variable does not satisfy the proportionality assumption, then we will exclude the variable from the model. However, the critical variables such as vaccination status and age will be kept in the model irrespective of the results of the test for proportionality assumption.

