2. SUMMARY OF THE ANALYTICAL PLANS

Objectives To evaluate protective efficacy of a single dose regimen of the bivalent, killed, whole cell oral cholera vaccine Shanchol™, given to healthy, non-pregnant residents aged one and above in Dhaka, Bangladesh, against culture-proven *V. cholerae* O1 diarrhea which has been detected in all treatment settings serving the catchment population with onset of 7 days to 6 months (180 days) after dosing

Design Two-arm individually randomized double-blind placebo-controlled trial

Subjects All enumerated healthy consenting subjects, residing in Wards 7-13, 15 and 41 of Mirpur, Dhaka, Bangladesh. Subjects will be included if they are permanent residents of the study site, not pregnant, and at least 1 year of age during vaccination.

Population size Approximately 350,000 subjects in the study area

Vaccination Period: January 10 to February 4, 2014

Agents Bivalent, killed, whole-cell oral cholera vaccine

End-points The primary endpoint for the study efficacy is the onset date of the first episode of culture-confirmed *V. cholerae* O1 diarrhea episodes detected in the study treatment centers with onsets of 7 days to 6 months (180 days) after dosing among those who have received one complete and correct dose of the vaccine or placebo.

Period of study 6 months post-receipt of either vaccine or placebo

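### The clock for non-recipients starts on the first campaign day, so their cholera is counted while dosing was still under way and who is a non-recipient depends on later dosing

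*Supplement*

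**What the plan says.** SAP section 2 gives the vaccination period as "January 10 to February 4, 2014". The protocol, under Delivery of study agent, adds: "Immunization will be carried to the study population in three phases". It gives no phase dates.

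SAP section 5 sets zero time as "The date of dose for the dose recipients and the start date of the mass vaccination (January 10, 2014) for non-dose recipients". The same section defines:
- follow-up: "The time between 7 and 180 days after the zero time";
- no-dose recipients: "Individuals who were present at zero time but not dosed";
- pre-dosing period: "The period on or before the zero time. Events whose onsets occur in this period will not be considered in the analysis".

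The protocol's secondary efficacy endpoints include first O1 cholera, and first O1 cholera with severe dehydration, "in non-participating subjects, who are detected within one of the study treatment centres". Counting starts 7 days after participants were dosed and runs to 6, 12, 18 and 24 months. Under Primary Analysis at 6 months the protocol also lists indirect, overall and total protection. SAP sections 6.1 and 6.2 cover direct protection only, with denominators limited to people who took a complete dose.

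On case confirmation, the cholera-episode definitions in the protocol (Efficacy assessment and endpoints) and in SAP section 4 both require an identity check and do not limit it to recipients. The protocol's Follow-up visits paragraph reads: "The residence of all participants who were culture confirmed for cholera will be visited within 14 days".

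**The concern.** Recipients start at their own dose. Non-recipients all start on the first day of a campaign lasting nearly four weeks. Two things follow.

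First, early counted time in non-recipients comes before many of their neighbours were dosed. It cannot carry a herd effect from those neighbours, so any such effect is diluted.

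Second, non-recipient status is settled by what happens after the clock starts. A resident who falls ill on 20 January, before the campaign reaches them, and is then never dosed becomes a non-recipient with a counted event. If that resident is dosed later, the event is dropped as pre-dosing. Someone who stays well and is dosed on 4 February adds none of their earlier event-free time to the non-recipient group. The inclusion criteria require participants to be healthy, so illness plausibly lowers the chance of being dosed. In that case incidence in non-recipients is pushed upward.

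At stake are the protocol's non-participant endpoints and any overall-protection estimate that includes non-recipients.

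**Working it through.** **Inputs.** Campaign dates: SAP section 2. Zero time and counting window: SAP section 5. Incidence of 0.56 per 1,000 per six months, 204,438 to be vaccinated and 324,178 to be enumerated: protocol, Sample size calculation. About 350,000 in the study area: SAP section 2.

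**Check of the plan's own figures.** The protocol's formula with p2 = 0.00056, p1 = 0.00028, R0 = 0.90, R = 0.50, k = 0.5, one-sided alpha 0.05 and power 0.80 gives N = 191,659, against 191,660 stated. Then 191,660 / (1 − 0.0625) = 204,437, against 204,438. The incidence input is therefore read correctly. The timing point does not depend on it.

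**Dates (10 January = day 0)**
- Last dosing day: 4 February = day 25, so the campaign spans 26 calendar days.
- Non-recipients are counted from day 7 (17 January) to day 180 (9 July): 180 − 7 + 1 = 174 days.
- The last-dosed reach their own day 7 on day 32 (11 February).

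**Overlap**
- Counted days while dosing continued: days 7 to 25 = 19; 19/174 = 10.9%.
- Counted days before the last-dosed reached day 7: days 7 to 31 = 25; 25/174 = 14.4%.
- If dosing was spread evenly over the 26 days (assumption), the average time in the window with neighbours not yet 7 days past dose is 12.5 days; 12.5/174 = 7.2%. With neighbours not yet dosed at all it is 6.6 days; 6.6/174 = 3.8%.
- These shares are for the six-month window. They shrink with longer follow-up: to day 365 there are 359 counted days, and 25/359 = 7.0%.

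**Match with the protocol endpoint.** On 17 January only people dosed on 10 January had reached day 7. Under even dosing that is 1/26, about 4% of recipients, and 18/26, about 69%, had not yet been dosed.

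**Illustrative case counts** (placebo incidence applied to non-recipients and spread evenly over 180 days; the documents give neither non-recipient incidence nor seasonality)
- Non-recipients: 324,178 − 204,438 = 119,740, or 350,000 − 204,438 = 145,562.
- Expected over 180 days: 119,740 × 0.00056 = 67, or 145,562 × 0.00056 = 82.
- In the 19 days of continuing dosing: 67 × 19/180 = 7.1, or 82 × 19/180 = 8.7.
- Corresponding to the 12.5-day average: 67 × 12.5/180 = 4.7, or 82 × 12.5/180 = 5.7.

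**Scale of the sorting effect.** Future recipients would have about 204,438 × 0.00056 × 6.6/180 = 4 cases between 17 January and their dose under even dosing. Only cases in people whom illness then kept from being dosed are moved into the non-recipient group. The documents give no figure for that fraction.

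**The case against.** The strongest reply is that little depends on this definition. The SAP specifies no analysis of non-recipients. The protocol names no comparator for its non-participant endpoints and does not define the overall contrast. Cases in people dosed later are already excluded, and the overlap is modest. The protocol's start point could also be read as the start of dosing, and the flowcharts for population assembly and date assignment are not shown. This limits the size and reach of the point. It does not remove it: the SAP's primary and severe-cholera analyses make no use of a non-recipient zero time, so the definition can matter only for these protocol endpoints, and it is the only SAP guidance for them.

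Four stronger readings are tempting and are not supported.
- *Non-recipient cases escape the identity check.* Both episode definitions require the check without restriction. The home visit is worded for participants, whom the protocol's Project Summary describes as dose recipients, but its census section uses the word more loosely, for people given an ID after enumeration. This is wording to reconcile, not a stated omission.
- *The indirect-protection estimate is distorted by this rule.* The only description of the GIS method, in the response to external reviewer 1 (comment 9) attached to the 2012 protocol, contrasts placebo recipients in high- and low-coverage neighbourhoods. Their clock starts at their own dose.
- *Cases of everyone not yet offered a dose are counted.* Only those of people never dosed afterwards are.
- *About 9 of 67 expected cases are affected (67 × 25/180).* That applies the last-dosed worst case to everyone; the average under even dosing is about 5.

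A later start also has a price: it shifts the calendar window in a setting that the protocol describes as having biannual outbreaks.

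**Conclusion.** The point holds for the protocol's non-participant secondary endpoints and for any overall-protection estimate that includes non-recipients. The SAP's common start date does not match a count that begins 7 days after participants were dosed, and it lets later dosing decide group membership.

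The date arithmetic is firm: 19 of 174 counted days (11%) overlap dosing, and 25 (14%) precede day 7 for the last-dosed. The 7% average rests on even dosing, and the case counts rest also on even incidence at the placebo rate. The sorting effect is structural. Its upward direction depends on illness reducing the chance of being dosed, and its size cannot be computed from the documents.

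The randomised vaccine-versus-placebo comparison is untouched. On the only description given, so is the GIS contrast among placebo recipients. The bias is real but modest, and cheap to remove.

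**What to change.** In SAP section 5, for the non-participant endpoints and any overall estimate only, start non-recipients at a landmark: the last vaccination day, 4 February 2014. Include only people alive, resident and undosed on that date, and count events from day 7 to day 180 after it. The last day of the phase that covered each person is an alternative, but it needs phase dates, a way to assign undosed people to phases, and a rule for anyone dosed afterwards. Leave zero time unchanged for the primary analysis and the covariates.

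The cost is one definition and one date in code. With the 4 February landmark, counting runs from 11 February to 3 August. The first 25 counted days are dropped, about 9 to 11 cases at even incidence (67 or 82 × 25/180), and 25 days are added at the end. Recipients' windows range from 17 January to 9 July for the first-dosed to 11 February to 3 August for the last-dosed, so any comparison with them should account for calendar time. One way is to restrict it to the 149 days common to all, 11 February to 9 July.

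Separately, reconcile the protocol's Follow-up visits paragraph with the two episode definitions, so that the same identity check is stated for non-recipient cases. Do not remove the check from either group.

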- To evaluate protective efficacy of a single dose regimen of a bivalent, killed, whole cell-based oral cholera vaccine Shanchol™, given to healthy, non-pregnant residents one year and older over the period of 7 days to 12 months, from 7 days to 18 months and 7 days to 24 months after dosing against:
 - Culture-proven *V. cholerae* O1 diarrhea with severe dehydration detected in treatment centres

- Culture-proven *V. cholerae* O139 diarrhea, detected in treatment centres
- Culture-proven *V. cholerae* O139 diarrhea with severe dehydration detected in treatment centres
- To evaluate protective efficacy of the single dose regimen of Shanchol™ against acute watery diarrhea detected in treatment centres with onset of 7 days to 6 months, 7 days to 12 months, from 7 days to 18 months and 7 days to 24 months after dosing
- To evaluate protective efficacy of the single dose regimen of Shanchol™ against acute watery diarrhea with severe dehydration detected in treatment centres with onset of 7 days to 6 months, 7 days to 12 months, from 7 days to 18 months and 7 days to 24 months after dosing
- To evaluate serum vibriocidal (to El Tor Inaba and Ogawa serogroup O1 and to serogroup O139 organisms) antibody responses to a single dose regimen of the bivalent, killed, whole cell-based oral cholera vaccine Shanchol™ in healthy, non-pregnant residents, aged one year and older in a subset of population
- To evaluate the safety up to 28 days following a single dose of the bivalent, killed, whole cell oral cholera vaccine Shanchol™ administered to healthy, non-pregnant residents one year and older.

Background of the Project including Preliminary Observations

Provide scientific validity of the hypothesis based on background information of the proposed study and discuss previous works on the research topic, including information on sex, gender and diversity (ethnicity, SES) by citing specific references. Critically analyze available knowledge and discuss the questions and gaps in the knowledge that need to be filled to achieve the proposed aims. If there is no sufficient information on the subject, indicate the need to develop new knowledge.

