The DSMB will also be responsible for un-blinding the randomization number codes in the event of severe putative vaccine reactions. Otherwise, the codes will not be revealed until the end of the trial and until the computerized dataset has been frozen. If the intervention assignment is un-blinded, all study collaborators will be notified immediately.

Measurements

Census update

The census in the study population will be updated every six months after intervention with the study agents. During this process in-migrants within the study area will get a SCVB card with unique ID to ease the disease surveillance process. Data collectors will visit each house in the intervention areas and collect information on births, deaths, migrations (in/out), missed in previous census, change in marital status, pregnancies and other events (Appendix 1D).

Disease Surveillance

1. Surveillance at the icddr,b hospitals in Mohakhali and Mirpur

All patients from the study area presenting for care at the hospital with diarrhea will be included in routine hospital surveillance. A diarrhoeal visit is defined as a visit by a patient who has in the 24 h before presentation, three or more loose or liquid stool or at least 1 bloody loose stool or any number of loose stools with signs of dehydration present, as stated in criteria used at the icddr,b hospitals[29]. The assessment of dehydration status in diarrhea will be carried out by trained personnel.

The diarrheal disease surveillance for the project will be conducted at icddr,b hospitals at Mohakhali and Mirpur and other health facilities for patients coming from the Mirpur study area (wards 7-13, 15 and 41). Clinical staff at each of the two hospitals and other facilities will evaluate each patient at the hospital triage area and provide treatment as per the routine procedure. Internal clinical monitoring for quality control will also be carried out for hospitalized study patients using a disease surveillance questionnaire (Appendix 2B). Around 5% of the study patients will be further evaluated immediately after admission. A trained physician will function as the safety monitor for the study and will oversee

clinical procedures for patient enrolment and management during surveillance to monitor GCP practice and trial conduct.

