adverse events and serious adverse events in this subgroup who received 1 dose of vaccine or placebo and present for care of vaccine adverse effects at treatment settings or who die from the time of dosing until 28 days after dosing to be captured every 2 weeks active surveillance via solicited questionnaires. For this purpose, trained medical personnel will visit homes of participants every two weeks to collect medical history and assess the safety of the study agent.

Verbal Autopsy:

We will carry out 'Verbal Autopsy' in our study area where deaths will be identified through a household search by home visits which will be conducted by study staff. Verbal autopsy will be conducted on death cases identified by this procedure. The aim of the 'Verbal Autopsy' is to identify the number of deaths and the probable causes of death in this time period after receiving the investigational product. Consent will be obtained from a relative of the dead participant (Appendix 13A). We will use adopted WHO verbal autopsy questionnaire[44] to conduct verbal autopsy, (Appendix 13B). After identification, trained medical professional will visit homes of the deceased to perform verbal autopsy.

Sample Size Calculation and Outcome (Primary and Secondary) Variable(s)

Clearly mention your assumptions. List the power and precision desired. Describe the optimal conditions to attain the sample size. Justify the sample size that is deemed sufficient to achieve the specific aims.

Sample size calculation for primary analysis

In this placebo-controlled individually randomized trial, the primary analysis is to evaluate efficacy of the vaccine after six months following vaccination. Even this trial design is to test the conventional null hypothesis of no difference, a criterion that a confidence limit for relative risk is assumed less than a specified value for monitoring the outcome at six month. Therefore, we wish to show that the ratio of risk in population 1 (treatment group) to risk in population 2 (placebo group) is less than specific relative risk rather than 1. The usual null value of relative risk (R_0) is, therefore, required to be excluded by the pre-specified value, say 0.10; thus, the R_0 becomes 0.90 (1.00-0.10).

The sample size, N , for this study is, therefore, calculated based on logarithmic transformation method described elsewhere (Blackwelder, 1993) using the following formula

$$N = (z_\alpha + z_\beta)^2 [q_1/kp_1 + q_2/(1-k)p_2] / (\log R_0 - \log R)^2$$

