3. POPULATION AND DEMOGRAPHIC EVENTS

A census was conducted by the project people during July 2012 to December 2013 to enumerate the study area population. The census captured the *de jure* population defined as persons who stated their residence in the study area was their regular residence. The population has been regularly updated thorough vital demographic events of the study area population. A close out census will be conducted after six months of follow-up.

Out-migrations (internal/external): Individuals who were present at zero time (defined in Chapter 5: Other definition),but migrated out any time after zero time.

Deaths: Individuals who were present at m but died any time after zero time.

For the analysis, we will follow the demographic date assignment flow chart (Appendix 5).

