6. THE ANALYSES

6.1. Primary analysis (direct protection against severe and non-severe cholera)

This primary analysis will compare subjects according to the study agent actually received and will include only those subjects who satisfied the inclusion/exclusion criteria, followed the protocol, and received one complete dose.

Onset of follow-up for counting events: All cholera episodes will be included if they have onsets between 7 and 180 days after the zero time.

Direct protection is estimated by comparing the incidence of cholera among vaccine recipients and the incidence of the cholera among placebo recipients.

Numerator events for analysis: Numerator events will be cholera episodes (defined above) whose onsets are between 7 and 180 days after the zero time. Cholera cases that occur between the zero time and the beginning of follow-up (zero time +7 days) will not be considered as a cholera episode and will not be included in this analysis.

Denominator for analysis: Subjects in the denominator for analysis are those who completely ingested dose of the agent and were at least 12 months of age at zero time and were otherwise eligible and were noted as having received either oral cholera vaccine or placebo. In analyses of time-to-event, the person-time at risk begins at the zero time and continues until the date of death, date of out-migration, date of event under analysis, or to zero time +180 days for this analysis.

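### Deaths are sought by house visits and verbal autopsy in both arms, but the only death endpoint stops at day 28 and cites passive surveillance, and no mortality comparison by arm is planned

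*Supplement*

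**What the plan says.** **Finding deaths.** In the latest protocol (Census update), data collectors visit each house every six months and "collect information on births, deaths, migrations (in/out), missed in previous census". Under Verbal Autopsy, study staff search households for deaths. The aim is "to identify the number of deaths and the probable causes of death in this time period after receiving the investigational product". That period is not defined. SAP section 3 defines deaths as persons present at the start "but died any time after zero time" and plans a close-out census after six months of follow-up.

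**Counting deaths.** The safety objective is "To evaluate the safety up to 28 days following a single dose of the bivalent, killed, whole cell oral cholera vaccine". The Secondary safety endpoints cover adverse events in participants who present for care or "who die from the time of dosing until 28 days later (passive surveillance by type of complaint and by cause of death". Under Active follow up for safety, 6,000 participants are contacted every two weeks to day 28, and deaths among them are captured.

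**Using deaths in the analysis.** SAP section 5 has "Lost to follow up: Individuals who died or moved out of the study area from the resident any time after zero time". SAP section 6.1 says that "the person-time at risk begins at the zero time and continues until the date of death, date of out-migration, date of event under analysis"; failing any of these, it stops at day 180. Section 6.2 repeats this for severe cholera. No mortality or safety analysis appears in SAP sections 2 to 9. The protocol's list of additional analyses at six months has none either.

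**The concern.** Death is the gravest safety outcome, and 1:1 randomisation by vial in more than 200,000 people gives an unbiased comparison of it. The plan pays for good ascertainment of deaths but gives the result no endpoint, denominator or method.

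Two things are at stake. First, if the 28-day endpoint is followed as written, a participant outside the 6,000 who dies at home may not come to notice through treatment settings, so the count may be too low. Second, deaths after day 28 have no pre-specified comparison. Any comparison made later would be post hoc, whichever way it pointed.

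**Working it through.** **1. Arm size.** The protocol's formula is N = (z_α + z_β)² [q1/(k·p1) + q2/((1−k)·p2)] / (log R0 − log R)². Its inputs are p2 = 0.00056, p1 = 0.00028, R0 = 0.90, R = 0.50, k = 0.5, one-sided α = 0.05 and power 0.80. This gives 191,659.2, or 191,660 rounded up, as stated. Dividing by (1 − 0.0625) gives 204,437.3, which matches the stated 204,438, or 102,219 per arm. Nothing below disputes these figures; they only supply the arm size.

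**2. Coverage of the death endpoint.**
- Active capture: 6,000 / 204,438 = 2.9% of those dosed.
- Share of the 180-day primary period: 28 / 180 = 16%.
- Share of the 24-month follow-up: 28 / 730 = 4%.

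**3. Where each source of deaths leads.**

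| Source | Window stated | Endpoint named | Comparison by arm |
|---|---|---|---|
| Passive surveillance | 28 days | Yes | None described |
| Active follow-up of 6,000 | 28 days | Same outcomes, subset only | None described |
| Household search and verbal autopsy | Undefined | No | None described |
| Six-monthly census | Throughout | No (censoring date only) | None described |

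**4. Timing.** The SAP gives dosing as 10 January to 4 February 2014, so the last 28-day window closed on 4 March 2014. The version history log dates approval of the verbal-autopsy addendum to 19 March and 17 April 2014. The search could still find earlier deaths in retrospect. But the text does not say whether it was meant to complete the 28-day endpoint or to cover a longer period.

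**5. Illustration of size.** The documents give no death rate, so 3 to 6 deaths per 1,000 per year is assumed. Attrition is 25% a year, from the protocol, applied as a constant rate L = −ln(0.75) = 0.2877.
- Person-years per arm = 102,219 × (1 − e^(−L·t)) / L.
- Deaths D = rate × person-years.
- The 95% CI around a true ratio of 1 is exp(±1.96·√(2/D)).

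| To | Person-years per arm | Deaths per arm | 95% CI at ratio 1 |
|---|---|---|---|
| Day 28 | 7,756 | 23 to 47 | 0.56–1.78 to 0.67–1.50 |
| Day 180 | 46,997 | 141 to 282 | 0.79–1.26 to 0.85–1.18 |
| 24 months | 155,452 | 466 to 933 | 0.88–1.14 to 0.91–1.10 |

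The protocol also states attrition of 6.25% for six months. With that figure, person-years to day 180 are 102,219 × (180/365) × (1 − 0.0625/2) = 48,834, and deaths are 147 to 293 per arm. The picture does not change.

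**The case against.** **Deaths are not ignored.** Death to day 28 is part of a listed safety endpoint in vaccine and placebo recipients. Death during protocol-defined surveillance is also a serious adverse event, reported within 24 hours. The DSMB receives the randomisation identities in sealed envelopes and reviews accumulated safety data. This stands. A reader might infer that deaths are never compared. The documents support only that no comparison by arm is described.

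**The 28-day count need not be passive only.** The active cohort captures deaths, and the verbal-autopsy period could be read as the 28 days named just before it. Nothing bars deaths found by household search from the endpoint. This stands in part: the reading is possible, but the endpoint names passive surveillance and the link is not written down.

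**Censoring at death is ordinary.** This stands fully. The definition of loss to follow-up is not itself a fault, and the SAP names death and out-migration separately in sections 3 and 6.1. A reader might infer that deaths vanish into a pooled row dominated by migrants. That cannot be supported, because the CONSORT chart and the demographic flowchart are figures that are not shown.

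**Scope.** The SAP as shown is a six-month efficacy plan without any adverse-event analysis. Its overview is not available, and the protocol says that a Data and Safety Monitoring Plan will be made. So the SAP's silence is not specific to death. But the protocol, which does set safety endpoints, has no mortality comparison either.

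**The 28-day objective is deliberate.** The protocol describes extensive safety documentation for this vaccine, so omitting longer-term mortality contradicts no stated objective. This stands, and it makes the point an improvement to the plan rather than an error in it.

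**Conclusion.** The concern holds as a worthwhile, cheap improvement. As written, the 28-day death endpoint rests on passive surveillance, with active capture in 2.9% of participants. The verbal-autopsy window is undefined. Deaths after day 28 enter the SAP only as censoring, and no comparison by arm is planned. None of this touches the efficacy analysis.

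Under the assumed 3 to 6 deaths per 1,000 per year, extending the comparison from day 28 to day 180 raises expected deaths per arm about sixfold (46,997 / 7,756 = 6.1). The confidence interval around no difference narrows from roughly 0.56–1.78 to 0.79–1.26 at the lower rate, and from 0.67–1.50 to 0.85–1.18 at the higher. These figures rest on a death rate that is not in the documents and on near-complete capture of deaths by the house visits. The gap in the plan does not depend on them.

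**What to change.** 1. **Protocol, Secondary safety endpoints:** take 28-day deaths for all dosed participants from every source: household search, census, verbal autopsy, and passive and active surveillance.
2. **Protocol, Verbal Autopsy:** state the start and end of the period covered, and that it feeds the endpoint in item 1 and the analysis in item 3.
3. **SAP section 6 (or a separate safety plan):** add a secondary safety analysis of all-cause deaths in everyone dosed, by randomised arm from the vial number, to day 28 and day 180 and repeated at later time points. Give counts, person-time and a rate ratio or hazard ratio with a two-sided 95% CI, plus a table of verbal-autopsy causes by arm.
4. **SAP sections 3 and 5:** report deaths separately from out-migration, by arm. Keep censoring at death in the cholera Cox model.

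The cost is a change of wording, one estimate and one table. No new visits or data are needed. The downside is one more safety comparison to report and interpret.
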